## **1. PURPOSE OF THE STUDY**

#### a. Brief Summary

The overarching goal of our project is to establish a novel, non-invasive, immediately clinically applicable imaging test for the diagnosis of bone tumors, including primary malignant bone tumors, metastases, as well as benign bone lesions, osteonecrosis and infection/non-cancer inflammatory processes. The purpose of this project was to evaluate imaging characteristics of osteonecrosis before and after decompression surgery with ferumoxytol-enhanced MRI. Our approach relies on the FDA-approved iron supplement drug ferumoxytol (Feraheme), which is used in patients for intravenous treatment of iron deficiency. Ferumoxytol is composed of iron oxide nanoparticles, which provide a strong T1- and T2-signal on magnetic resonance (MR) images and, thus, can be used as an MR contrast agent. Based on our extensive experience with pre-clinical and clinical imaging applications of iron oxide nanoparticles, we hypothesize that MR images after intravenous injection of ferumoxytol will improve lesion detection and characterization compared to conventional unenhanced and Gd-enhanced MRI scans.

#### b. Objectives

 We hypothesize that MR images after intravenous injection of ferumoxytol will improve the detection of osteonecrosis lesions compared to standard MRI scans.
 We hypothesize that ferumoxytol-T2-enhancement of osteonecrotic bone lesions on MR images correlates with the quantity and distribution of healthy bone marrow cells in the lesion.

3. We hypothesize that ferumoxytol-enhanced MRI will improve evaluation of therapy success of osteonecrosis after decompression surgery.

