## 2. STUDY PROCEDURES

#### a. Procedures

Screening will occur during a regular clinic visit. Each participant will undergo an MRI after a single intravenous injection of ferumoxytol at a dose of 5 mg Fe/kg body weight. Precontrast images will be added when feasible. Postcontrast images will be obtained directly after and/or 1-2 days after ferumoxytol administration. In patients with osteonecrosis who undergo a surgical decompression procedure with implantation of bone marrow derived cells into the osteonecrosis, a ferumoxytol-enhanced MRI will be performed before surgery and follow up MR scans will be obtained at 1-6 months after the surgery. When available, routinely obtained biopsy and/or surgical resection samples of bone lesions will be examined by our collaborating pathologist for presence of mesenchymal stromal cells, macrophages and possibly iron content in samples that happen to be obtained shortly after the ferumoxytol injection.

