## 10. STATISTICAL PLAN

All experiments were analyzed using R version 3.4.4. The number of patients per experimental group were determined by power analyses. Signal-to-noise ratios (SNR) and T2 relaxation times were pairwise compared between osteonecrosis lesions with and ferumoxytol administration, and between decompression track areas with and without visible iron-labeled cells, using a mixed-effects model including a random effect term accounting for correlation among the measures within a same patient. A Fisher exact test was applied for comparison of clinical outcomes of osteonecrosis with and without ferumoxytol enhancement. In addition, differences in time to progression of osteonecrosis from surgery between bone lesions that did or did not enhance with ferumoxytol were assessed by log-rank tests. Because of the small sample size and exploring purpose of this study, a P < 0.05 without adjustment for multiple comparisons was considered to indicate significant differences between experimental groups.

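### Hypothesis 2 concerns the quantity and distribution of healthy marrow cells, but tissue is read only for presence of cell types and no planned analysis uses it

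*Combined protocol and SAP*

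**What the plan says.** Section 1.b (Objectives) lists three hypotheses. The second is that "ferumoxytol-T2-enhancement of osteonecrotic bone lesions on MR images correlates with the quantity and distribution of healthy bone marrow cells in the lesion".

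Section 2.a (Procedures) describes the only tissue source: "When available, routinely obtained biopsy and/or surgical resection samples of bone lesions will be examined by our collaborating pathologist". The examination is "for presence of mesenchymal stromal cells, macrophages and possibly iron content in samples that happen to be obtained shortly after the ferumoxytol injection". The section gives no count, grade, measure of distribution or criterion for a healthy cell, and does not match the sample site to an MR region. It also makes precontrast imaging conditional on feasibility.

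Section 2.g (Study Endpoints) names MR signal characteristics of osteonecrosis as the endpoint. The secondary endpoint is MR features of response to decompression surgery and stem cell transplant. Neither involves histology.

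Section 10 (Statistical Plan) compares SNR and T2 between lesions by ferumoxytol administration and "between decompression track areas with and without visible iron-labeled cells, using a mixed-effects model". It then gives a Fisher exact test of clinical outcomes and a log-rank test of time to progression, both by ferumoxytol enhancement.

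**The concern.** A claim that T2 enhancement tracks the quantity and distribution of healthy marrow cells needs two things. One is a cell measure obtained independently of the MR signal. The other is an analysis relating that measure to T2. The plan has neither: the tissue reading records presence, and it enters no analysis. Expanding the existing text would not close this gap, because both the measurement and the analysis have to be added.

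At stake is what can be said about hypothesis 2 at the end. Followed exactly, the plan yields no result for it. The secondary risk is that the track-area comparison, the only analysis that mentions cells, is later cited in its place.

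**Working it through.** **Step 1: match each Section 10 analysis to hypothesis 2.**

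| Section 10 analysis | Tissue variable? | Cell quantity or distribution? | Region |
|---|---|---|---|
| SNR and T2 by ferumoxytol administration | No | No | Lesion |
| SNR and T2 by visible iron-labelled cells | None named | No, binary | Decompression track |
| Fisher exact test, clinical outcomes by enhancement | No | No | Lesion |
| Log-rank test, time to progression by enhancement | No | No | Lesion |

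None of the four uses a stated tissue variable, and none is a correlation or regression on cell quantity.

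**Step 2: can the second analysis stand in?** It compares T2 and SNR "between decompression track areas with and without visible iron-labeled cells".
- The grouping is yes or no, while the hypothesis is about quantity and distribution.
- The region is the surgical track. Under Section 2.a, bone marrow derived cells are implanted at that surgery, so labelled cells there need not be the lesion's own marrow cells.
- The modality behind the word visible is not stated. MRI is a reasonable inference: Section 10 names no tissue, and Section 2.a follows patients after surgery by MR. On that reading, Section 3.a matters, because it says ingested iron oxide darkens T2-weighted images. Sorting areas by visible iron and then comparing T2 and SNR would partly restate the sorting rule. If microscopy were meant, the circularity would fall away, but the first two limits would remain.

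**Step 3: what could an added correlation show?** Section 10 says group sizes came from power analyses but gives no power, effect size or SD, and no sample size is stated for hypothesis 2, so there is no plan figure to reproduce.

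Inputs:
- Upper limit on patients: 10, the size of the ferumoxytol group (Section 6.a).
- Number with tissue: not given. Assumed range 5 to 10, one sample per patient.
- Alpha: 0.05 (Section 10), assumed two-sided.

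Critical Pearson correlation: r = t / √(n − 2 + t²), with t the two-sided 5% point on n − 2 df.
- n = 5: t = 3.182; r = 3.182 / √(3 + 10.13) = 0.88.
- n = 10: t = 2.306; r = 2.306 / √(8 + 5.32) = 0.63.

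95% CI by Fisher z, tanh(atanh(r) ± 1.96/√(n − 3)), for an illustrative observed r = 0.6 (assumed; atanh = 0.693).
- n = 5: 0.693 ± 1.386, giving −0.60 to 0.97.
- n = 10: 0.693 ± 0.741, giving −0.05 to 0.89.

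Smallest true r detectable with 80% power: tanh((1.960 + 0.842)/√(n − 3)).
- n = 5: tanh(1.981) = 0.96.
- n = 10: tanh(1.059) = 0.79.

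These are Pearson formulas. They indicate the order of precision and do not describe exactly the rank correlation or mixed model proposed under the fix.

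**The case against.** The strongest reply is that Section 10 never offers the track comparison as the test of hypothesis 2. It fits hypothesis 3 and the secondary endpoint on treatment response at least as well. This stands. A reader might infer that the plan would manufacture support for hypothesis 2 from MRI alone, using areas chosen because they are dark. The documents do not support that. They do not link the comparison to hypothesis 2, state the modality or describe selection by darkness. What they show is a hypothesis without an analysis; the circularity is conditional on the MRI reading.

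Second, the study calls itself exploratory, histology is not an endpoint and tissue is opportunistic. This is true, and it limits how much can be asked. It does not supply the missing measurement or analysis, and the hypothesis is still listed as one of three.

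Third, the correlation figures measure the imprecision of an added analysis, not the cost of omitting it, and they rest on assumed tissue counts. That is right. They are given to set expectations and to argue for an estimate with an interval over a significance test.

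Fourth, a cell count alone would not address distribution, sample site or timing. That also stands, and the fix covers those items.

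**Conclusion.** The point holds as a mismatch between hypothesis, measurement and analysis. Hypothesis 2 is about quantity and distribution, the tissue reading is about presence, and none of the four planned analyses uses tissue. The plan as written cannot test it. This conclusion needs no assumption about how iron visibility is judged.

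The track-area comparison should not be cited as evidence for hypothesis 2, because it is binary and in a different region. Partial circularity is a further reason only if visibility means visibility on MRI.

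Even with the gap closed, precision would be poor. With an assumed 5 to 10 patients and one sample each, significance at two-sided 0.05 would need |r| of about 0.88 down to 0.63. The change is worth making, but it supports an exploratory estimate and no more.

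**What to change.** **Section 2.a.** On the samples already planned for examination, have the pathologist give a graded or counted score for marrow cells, with healthy defined, and a simple distribution score where the sample allows. Record the sample site and the time since injection.

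**Section 10.** For lesions with tissue, relate lesion T2 in the region matching the sample to that score. Use postcontrast T2, or T2 change where precontrast images exist. Use rank correlation, or a mixed model with patient as random effect if patients contribute several lesions. Report the number of lesions and patients with tissue and the estimate with its CI, labelled exploratory. State that the track-area comparison is not evidence for hypothesis 2. If usable tissue is too sparse, report hypothesis 2 as not tested.

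**Cost.** Modest extra scoring and site matching, one extra analysis, and a weaker claim. No new biopsies are needed.

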## e. Alternative Procedures or Courses of Treatment

The current alternative diagnostic methods are: biopsy, which is invasive, painful, and frequently inadequate; Conventional MRI without an iron nanoparticle contrast, which cannot distinguish healthy and necrotic cells in osteonecrosis; PET/CT/Xray, which add exposure to ionizing radiation. The current standard of imaging is an MRI; the addition of an iron nanoparticle contrast agent is expected to make this test more sensitive and

specific. No standard treatment will be withheld, and the standard of care diagnostic test is included in our research.

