## g. Study Endpoint(s)

Endpoint of these examinations is to define distinctive MR signal characteristics of osteonecrosis lesions. Secondary endpoint is to define specific ferumoxytol-MR imaging features that indicate treatment response to decompression surgery and stem cell transplant.

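### Objective 3 claims that ferumoxytol MRI improves the evaluation of therapy success, but no planned outcome analysis sets it against a standard-MRI assessment, so the plan can show association only

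*Combined protocol and SAP*

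**What the plan says.** Objectives (1.b) states the third hypothesis as "We hypothesize that ferumoxytol-enhanced MRI will improve evaluation of therapy success of osteonecrosis after decompression surgery". That sentence names no comparator. Objective 1, in the same section, does: it expects that ferumoxytol images "will improve the detection of osteonecrosis lesions compared to standard MRI scans".

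Study Endpoint(s) (2.g) is more modest: "Secondary endpoint is to define specific ferumoxytol-MR imaging features that indicate treatment response to decompression surgery and stem cell transplant". It makes no claim of superiority.

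The Statistical Plan (section 10) gives two analyses with an outcome. The first is "A Fisher exact test was applied for comparison of clinical outcomes of osteonecrosis with and without ferumoxytol enhancement". The second is a log-rank test of "differences in time to progression of osteonecrosis from surgery between bone lesions that did or did not enhance with ferumoxytol". It also plans mixed-effects comparisons of signal-to-noise ratio (SNR) and T2 relaxation time.

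On the availability of a comparator, Alternative Procedures (2.e) says that "the standard of care diagnostic test is included in our research". Procedures (2.a) makes precontrast images conditional on feasibility. Planned Enrollment (6.a) sets 10 patients with ferumoxytol and 10 without.

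**The concern.** A claim of improvement needs two assessments of the same thing, one by each method, judged against a common outcome. Here only one of the two enters an outcome analysis. If enhancing lesions do better than non-enhancing ones, that may be because enhancement carries new information. It may equally be because enhancement repeats what a reader would already see on the standard scan. The planned tests cannot separate these two explanations.

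What is at stake is what the trial may conclude. Benefits (section 8) already describes the method as better than the existing standard of care and says it can improve the prediction of successful treatment. Risk to Children (7.g) counts clarity about the success of surgery among the reasons to expect direct benefit. A significant association could be taken as support for these statements although nothing in the analysis tests them.

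**Working it through.** The plan gives no figure for this point, so there is none to reproduce. The check sets the claim against the analyses and then illustrates the gap.

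**Step 1. What each analysis in section 10 contains.**

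| Analysis | Split by | Outcome in it? | Standard-MRI judgement of response in it? |
|---|---|---|---|
| Fisher exact test | enhancement | yes, clinical outcome | no |
| Log-rank test | enhancement | yes, time to progression | no |
| Mixed model, SNR and T2 | lesions with and apparently without ferumoxytol (a word is missing) | no | no |
| Mixed model, SNR and T2 | track areas with and without visible labelled cells | no | no |

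A test of Objective 3 needs a row with a yes in both of the last two columns. There is none. No accuracy, reader or added-value analysis is described elsewhere.

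**Step 2. The other reading of the Fisher sentence.** It could mean the ferumoxytol group against the control group. That would compare how patients fare in the two groups, not how well either scan judges therapy. Eligibility Criteria (6.g) also lets patients with hemosiderosis or hemochromatosis enter the control group only, so the groups differ by design.

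**Step 3. Association without improvement.** All inputs are assumptions; the documents give none of them. Half the lesions have a favourable standard-MRI grade and half enhance. Success is 80% with a favourable grade and 20% otherwise. Enhancement agrees with the grade in a share *a* of lesions, equally in both halves, and given the grade it carries no further information.

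- Success if enhancing = a × 0.80 + (1 − a) × 0.20
- Success if not enhancing = a × 0.20 + (1 − a) × 0.80
- Difference = (2a − 1) × 60 percentage points

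For a = 0.8: 0.8 × 0.80 + 0.2 × 0.20 = 0.68, and 0.8 × 0.20 + 0.2 × 0.80 = 0.32, a difference of 36 points.

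| Agreement a | Enhancing | Not enhancing | Difference |
|---|---|---|---|
| 0.6 | 56% | 44% | 12 points |
| 0.7 | 62% | 38% | 24 points |
| 0.8 | 68% | 32% | 36 points |
| 0.9 | 74% | 26% | 48 points |
| 1.0 | 80% | 20% | 60 points |

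At a = 0.8, enhancement calls the outcome correctly in 68% of lesions and the standard grade in 80%. A clear association thus coexists with a reading that is 12 points worse.

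**Step 4. The same in a hypothetical table.** Outcome by enhancement of 9 good, 1 poor against 2 good, 8 poor gives Fisher p = 0.005; enhancement is right in (9 + 8)/20 = 85%. If the standard reading is also right in 85% of these patients, with 2 discordant pairs each way, the exact McNemar p is 1.0.

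**Step 5. What a direct paired comparison could show at this size.** The exact two-sided McNemar p for k discordant pairs all in one direction is 2 × 0.5^k: 0.0625 for k = 5 and 0.031 for k = 6. With 10 pairs, p < 0.05 therefore needs at least 6 discordant pairs. With 6, 7 or 8, all must point the same way; with 9 or 10, one may go against (8 v 1: p = 0.039; 9 v 1: p = 0.021). If 5% of patients are discordant against ferumoxytol and 20% to 60% in favour (assumed), power with 10 pairs runs from 0.5% to 46%.

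**The case against.** The strongest reply is that the working plan is already at the level of association. The secondary endpoint seeks features that indicate response, the Fisher and log-rank tests fit that endpoint, and section 10 calls the study small and exploratory. On this view only one verb is out of line. This largely stands, and it is why the remedy is mainly wording. It does not remove the point: the exploratory purpose is offered as the reason for leaving alpha unadjusted, and it supplies no comparator.

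A second reply is that Alternative Procedures (2.e) holds conventional MRI unable to tell healthy from necrotic cells, so a scenario in which it already grades response well is unfair. That is the premise under study and cannot be assumed in its favour. It does show that the illustration depends on its inputs. Moreover, with one lesion per patient, the 68% v 32% difference would reach Fisher p < 0.05 in only about 12% of trials at 5 v 5 and 19% at 10 v 10. The example shows what a positive result would mean, not how likely one is.

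A reader might infer several stronger things, which the documents do not support:

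- That every planned test relates enhancement to outcome. The SNR and T2 models do not.
- That a paired test is readily available from existing scans. Precontrast images are taken only when feasible (2.a), Potential Risks (7.a) lists the follow-up MRI as without contrast, and no response grade or reading procedure is defined.
- That the gadolinium wording in Brief Summary (1.a) belongs to this point. The hypothesis there, that ferumoxytol images "will improve lesion detection and characterization compared to conventional unenhanced and Gd-enhanced MRI scans", concerns detection and characterization, not therapy evaluation. The documents also do not say what contrast the standard-of-care scan uses, so they do not establish that no such scan occurs.
- That the sponsor will report an association as improvement. No passage says so; the risk lies in the wording of Objective 3.

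**Conclusion.** The point holds for Objective 3. Followed exactly, the plan can show that enhancement is associated with outcome. It cannot show that ferumoxytol MRI improves on standard MRI in evaluating therapy success. This rests on what the analyses in section 10 contain and needs no numerical assumption.

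The gap has no size that can be estimated from the documents. Under the assumed inputs, a difference between enhancing and non-enhancing lesions of 12 to 60 points (36 at 80% agreement) is compatible with no added information. The planned data remain usable; what must change is the claim drawn from them.

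**What to change.** 1. Restate Objective 3 as an association aim in line with Study Endpoint(s) (2.g): whether ferumoxytol-MRI features are associated with treatment response after decompression surgery.
2. Limit the reported conclusion, and the statement on treatment outcomes in Benefits (section 8), to the same scope.
3. State in section 10 that no claim of improvement will be drawn from the Fisher or log-rank results.
4. Optional: where a patient has precontrast and ferumoxytol images from the same time point, show a per-patient cross-table of the two calls against outcome. The outcome must be determined independently of both calls, which needs care because Planned Duration (section 6) uses follow-up MRI to determine clinical outcomes. The table would be incomplete and imprecise, so present it as descriptive and not as a confirmatory test.

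Items 1 to 3 cost wording and a less favourable claim. Item 4 needs a defined response call and a re-reading of the images that exist.

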#### c. Rationale for Research in Humans

In vivo studies in human patients are needed because the biodistribution of ferumoxytol nanoparticles is different in humans compared to animals. We did and are performing additional studies in mouse models in order to minimize and optimize studies in human patients. MR signal effects of ferumoxytol are dependent on its ability to interact with human bone marrow cells and other target tissues. To assess the applicability of the iron supplement ferumoxytol as a contrast agent in patients, we must investigate humans.

## 2. STUDY PROCEDURES

#### a. Procedures

Screening will occur during a regular clinic visit. Each participant will undergo an MRI after a single intravenous injection of ferumoxytol at a dose of 5 mg Fe/kg body weight. Precontrast images will be added when feasible. Postcontrast images will be obtained directly after and/or 1-2 days after ferumoxytol administration. In patients with osteonecrosis who undergo a surgical decompression procedure with implantation of bone marrow derived cells into the osteonecrosis, a ferumoxytol-enhanced MRI will be performed before surgery and follow up MR scans will be obtained at 1-6 months after the surgery. When available, routinely obtained biopsy and/or surgical resection samples of bone lesions will be examined by our collaborating pathologist for presence of mesenchymal stromal cells, macrophages and possibly iron content in samples that happen to be obtained shortly after the ferumoxytol injection.

#### c. Use of Deception in the Study

No deception, N/A

#### d. Use of Audio and Video Recordings

No recording, N/A

## e. Alternative Procedures or Courses of Treatment

The current alternative diagnostic methods are: biopsy, which is invasive, painful, and frequently inadequate; Conventional MRI without an iron nanoparticle contrast, which cannot distinguish healthy and necrotic cells in osteonecrosis; PET/CT/Xray, which add exposure to ionizing radiation. The current standard of imaging is an MRI; the addition of an iron nanoparticle contrast agent is expected to make this test more sensitive and

specific. No standard treatment will be withheld, and the standard of care diagnostic test is included in our research.

